APPENDIX 6. CLASSIFICATION OF RESCUE THERAPY

This appendix outlines the algorithm for the Arena clinical team/medical reviewers to classify rescue therapies for ulcerative colitis (UC) in a blinded manner. This will help establish 1) intercurrent events for the efficacy estimands, and 2) whether a subject will be excluded from the Per Protocol Set(s). All rescue therapies identified by the medical reviewers per the algorithm below will be imported in programming. This process will be repeated until database lock and the list of all rescue therapies identified will be finalized before study unblinding.

Only medications and medical procedures reported on the electronic case report forms (eCRFs) can be assessed whether they are rescue therapy for UC. If the exposure happens in the follow-up period (beginning on or after the date of last study treatment administration), then it would not be considered as a rescue therapy. Impact of rescue therapy use in the analysis is timing-dependent, eg, if a subject starts a rescue therapy between their Week 12 and Week 52 endpoint assessments, then it may have potential impact on Week 52 endpoint analysis but will have no impact on Week 12 endpoints. The rules outlined below apply to both new use and increase in dose from Baseline.

Biologics with immunomodulatory properties

- Rule:
 - Any exposure after first dose
- List of medications
 - Anti-TNFs:
 - ADALIMUMAB
 - CERTOLIZUMAB
 - CERTOLIZUMAB PEGOL
 - GOLIMUMAB
 - INFliximab
 - Other Biologics:
 - USTEKINUMAB
 - VEDOLIZUMAB

Non-biologics with immunomodulatory properties

- Immunosuppressants
 - Rule to consider for Week 12 efficacy endpoints:
 - After first dose and up to and including Week 8: any increase from baseline for more than 5 days

- After Week 8: Any dose above baseline
- Rule to consider for Week 52 efficacy endpoints:
 - After Week 12 and up to and including Week 40: any increase from baseline for more than 5 days
 - After Week 40: Any dose above baseline
- List of medications
 - MERCAPTOPURINE
 - AZATHIOPRINE
 - TIOGUANINE
 - METHOTREXATE
 - METHOTREXATE SODIUM
- 5-ASA COMPOUNDS
 - Rules to consider for Week 12 efficacy endpoints:
 - After first dose and up to and including Week 8: any increase from baseline for more than 5 days
 - After Week 8: Any dose above baseline
 - Rules to consider for Week 52 efficacy endpoints:
 - After Week 12 and up to and including Week 40: any increase from baseline for more than 5 days

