 - After Week 40: Any dose above baseline
 - List of medications
 - MESALAZINE
 - BALSALAZIDE
 - BALSALAZIDE DISODIUM DIHYDRATE
 - BALSALAZIDE SODIUM
 - OLSALAZINE SODIUM
 - SULFASALAZINE
 - BECLOMETASONE W/MESALAZINE
 - Route
 - ORAL
 - RECTAL

- Other small molecule immunomodulatory active agents
 - Rule:
 - Any exposure after first dose
 - List of medications
 - CICLOSPORIN
 - TACROLIMUS
 - TOFACITINIB
 - TOFACITINIB CITRATE
- Systemic glucocorticoids
 - Systemic glucocorticoids given via oral or rectal routes of administration
 - Rule:
 - After first dose and up to and including Week 8: any increase from baseline for more than 7 days
 - After Week 8: Any dose above baseline
 - List of medications
 - BETAMETHASONE
 - BETAMETHASONE DIPROPIONATE
 - BETAMETHASONE SODIUM PHOSPHATE
 - DEXAMETHASONE
 - DEXAMETHASONE SODIUM PHOSPHATE
 - DEXAMETHASONE VALERATE
 - METHYLPREDNISOLONE
 - METHYLPREDNISOLONE SODIUM SUCCINATE
 - PREDNISOLONE
 - PREDNISOLONE SODIUM PHOSPHATE
 - PREDNISOLONE METASULFOBENZOATE SODIUM
 - PREDNISONE
 - TRIAMCINOLONE
 - HYDROCORTISONE
 - HYDROCORTISONE ACETATE

- HYDROCORTISONE BUTYRATE
- HYDROCORTISONE SODIUM SUCCINATE
- ROUTE
 - ORAL
 - RECTAL
- Systemic glucocorticoids given via parenteral routes of administration
 - Rule:
 - Any exposure after first dose
 - List of medications
 - BETAMETHASONE
 - BETAMETHASONE DIPROPIONATE
 - BETAMETHASONE SODIUM PHOSPHATE
 - DEXAMETHASONE
 - DEXAMETHASONE SODIUM PHOSPHATE
 - DEXAMETHASONE VALERATE
 - METHYLPPREDNISOLONE
 - METHYLPPREDNISOLONE SODIUM SUCCINATE
 - PREDNISOLONE
 - PREDNISOLONE SODIUM PHOSPHATE
 - PREDNISOLONE METASULFOBENZOATE SODIUM
 - PREDNISONE
 - TRIAMCINOLONE
 - HYDROCORTISONE
 - HYDROCORTISONE ACETATE
 - HYDROCORTISONE BUTYRATE
 - HYDROCORTISONE SODIUM SUCCINATE
 - ROUTE
 - INTRAVENOUS
 - INTRAMUSCULAR
- Topical Glucocorticoids

- Budesonide
 - Rule
 - Subjects not taking Budesonide at baseline:
 - After first dose and up to and including Week 8: more than 9 mg/day for one day or any exposure for more than 5 days
 - After Week 8: Any dose above baseline
 - Subjects taking Budesonide at baseline:
 - After first dose and up to and including Week 8: more than 9 mg/day for one day or any increase for more than 5 days
 - After Week 8: Any dose above baseline
 - List of medications
 - BUDESONIDE
 - List of Routes
 - ORAL
 - RECTAL
- Beclomethasone
 - Rule
 - Subjects not taking Beclomethasone at baseline:

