 - After first dose and up to and including Week 8: more than 5 mg/day for one day OR any exposure for more than 5 days
 - After Week 8: Any dose above baseline
 - Subjects taking Beclomethasone at baseline:
 - After first dose and up to and including Week 8: more than 5 mg/day for one day or any increase for more than 5 days
 - After Week 8: Any dose above baseline
 - List of medications:
 - BECLOMETASONE
 - BECLOMETASONE DIPROPIONATE
 - BECLOMETASONE W/MESALAZINE
 - Routes:
 - ORAL
 - RECTAL

- Other small molecule immunomodulatory active agents
 - Rules to consider for Week 12 efficacy endpoints:
 - After first dose and up to and including Week 8: any increase from baseline (including new use) for more than 5 days
 - After Week 8: Any dose above baseline
 - Rules to consider for Week 52 efficacy endpoints:
 - After Week 12 and up to and including Week 40: any increase from baseline (including new use) for more than 5 days
 - After Week 40: Any dose above baseline
 - List of medications:
 - CICLOSPORIN
 - TACROLIMUS
 - TOFACITINIB
 - TOFACITINIB CITRATE
- Systemic glucocorticoids
 - Systemic glucocorticoids given via oral or rectal routes of administration
 - Rules to consider for Week 12 efficacy endpoints:
 - After first dose and up to and including Week 8: any increase from baseline for more than 7 days
 - After Week 8: Any dose above baseline
 - Rules to consider for Week 52 efficacy endpoints:
 - After Week 12 and up to and including Week 40: any increase from baseline for more than 7 days
 - After Week 40: Any dose above baseline
 - List of medications:
 - BETAMETHASONE
 - BETAMETHASONE DIPROPIONATE
 - BETAMETHASONE SODIUM PHOSPHATE
 - DEXAMETHASONE
 - DEXAMETHASONE SODIUM PHOSPHATE
 - DEXAMETHASONE VALERATE

- METHYLPREDNISOLONE
- METHYLPREDNISOLONE SODIUM SUCCINATE
- PREDNISOLONE
- PREDNISOLONE SODIUM PHOSPHATE
- PREDNISOLONE METASULFOBENZOATE SODIUM
- PREDNISONE
- TRIAMCINOLONE
- HYDROCORTISONE
- HYDROCORTISONE ACETATE
- HYDROCORTISONE BUTYRATE
- HYDROCORTISONE SODIUM SUCCINATE
- Routes:
 - ORAL
 - RECTAL
- Systemic glucocorticoids given via parenteral routes of administration
 - Rule for Week 12 endpoint:
 - Any exposure after first dose up to Week 12
 - Rules for Week 52 endpoint:
 - After Week 12 and up to and including Week 40: more than one dose
 - Any exposure after Week 40
 - List of medications:
 - BETAMETHASONE
 - BETAMETHASONE DIPROPIONATE
 - BETAMETHASONE SODIUM PHOSPHATE
 - DEXAMETHASONE
 - DEXAMETHASONE SODIUM PHOSPHATE

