 - DEXAMETHASONE VALERATE
 - METHYLPREDNISOLONE
 - METHYLPREDNISOLONE SODIUM SUCCINATE
 - PREDNISOLONE

- PREDNISOLONE SODIUM PHOSPHATE
- PREDNISOLONE METASULFOBENZOATE SODIUM
- PREDNISONE
- TRIAMCINOLONE
- HYDROCORTISONE
- HYDROCORTISONE ACETATE
- HYDROCORTISONE BUTYRATE
- HYDROCORTISONE SODIUM SUCCINATE
- Routes:
 - INTRAVENOUS
 - INTRAMUSCULAR
- Topical Glucocorticoids
 - Rules for Week 12 endpoints:
 - After first dose and up to and including Week 8: any exposure above baseline (or new use) for more than 5 days
 - After Week 8: Any dose above baseline
 - Rules for Week 52 endpoints:
 - After Week 12 and up to and including Week 40: any increase from baseline for more than 5 days
 - After Week 40 any increase above baseline
 - List of medications:
 - BUDESONIDE
 - Routes:
 - ORAL
 - RECTAL
- Beclomethasone
 - Rules for Week 12 endpoints:
 - After first dose and up to and including Week 8: Any increase above baseline for more than 5 days
 - After Week 8: Any dose above baseline
 - Rules for Week 52 endpoints:

- After Week 12 and up to and including Week 40: Any increase from baseline for more than 5 days
- After Week 40 any increase above baseline
- List of medications:
 - BECLOMETASONE
 - BECLOMETASONE DIPROPIONATE
 - BECLOMETASONE W/MESALAZINE
- Routes:
 - ORAL
 - RECTAL

Medical procedures

- Leukocyte apheresis, other apheresis, and plasma exchange
 - Rule:
 - Any exposure after first dose
 - List of medical procedures
 - APHERESIS
 - LEUKAPHERESIS
 - COLECTOMY (partial or total)
 - SIGMOIDECTOMY
 - COLOSTOMY
 - ILEOSTOMY

Statistical Analysis Plan - non-PK part V1.0 - 28-Sep-2022

Electronic Signature Manifestation

This page is a manifestation of the electronic signature(s) used in compliance with the organization's electronic signature policies and procedures.

Signer Full Name	Meaning of Signature	Date and Time
PPD	Document Approval (I certify that I have the education, training and experience to perform this task)	27 Sep 2022 23:50:22 UTC
PPD	Document Approval (I certify that I have the education, training and experience to perform this task)	28 Sep 2022 00:04:48 UTC
PPD	Document Approval (I certify that I have the education, training and experience to perform this task)	28 Sep 2022 10:56:10 UTC

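### SAP Appendix 6 lists five rescue drug groups twice under incompatible rules, so a short course between Weeks 12 and 40 is rescue under one listing and not under the other

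*SAP*

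**What the plan says.** SAP 16.1.2 treats a subject who starts rescue medication for UC, or whose UC medication rises above its Baseline dose, as a known nonresponder at later timepoints. It refers to Appendix 6 for what counts as rescue. SAP 16.1.6 and 16.2.1 apply the same handling to the key and other secondary endpoints. Reviewers apply the appendix blinded: "All rescue therapies identified by the medical reviewers per the algorithm below will be imported in programming". The list is final before unblinding.

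Immunosuppressants and 5-ASA appear once, each with a Week 12 rule and a Week 52 rule. Five other groups appear twice.

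- **First listing.** One rule per group, with no endpoint named and no end date. For other small molecules (ciclosporin, tacrolimus, tofacitinib) and parenteral glucocorticoids it is "Any exposure after first dose". Oral or rectal glucocorticoids, budesonide and beclomethasone have duration or daily-dose triggers up to Week 8, then "After Week 8: Any dose above baseline".
- **Second listing.** Separate rules for Week 12 and Week 52 endpoints. The Week 52 rules are "After Week 12 and up to and including Week 40: any increase from baseline (including new use) for more than 5 days" for small molecules, "After Week 12 and up to and including Week 40: any increase from baseline for more than 7 days" for oral or rectal glucocorticoids, "After Week 12 and up to and including Week 40: more than one dose" for parenteral glucocorticoids and "After Week 12 and up to and including Week 40: any increase from baseline for more than 5 days" for budesonide. Beclomethasone has the same 5-day threshold.

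No sentence says that one listing replaces the other, or that they serve different purposes.

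**The concern.** The rescue definition is the working form of the intercurrent event in the primary estimand. With two rules for the same drug, two reviewers who both follow the appendix can classify one course in opposite ways. Three examples are rescue under the first listing and not under the second: tofacitinib for 4 days at Week 30, oral prednisolone above baseline for 3 days at Week 20, and one intravenous steroid dose at Week 20. The primary and all five key secondary endpoints depend on this classification. Sustained remission is exposed at both ends, because some Week 12 rules differ as well.

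A related point concerns events in the parent study. The Week 52 windows for immunosuppressants, 5-ASA and all five groups in the second listing open only after Week 12. SAP Table 1 counts intercurrent events before the efficacy assessment, and SAP 16.1.2 carries nonresponse to later timepoints. The plan does not reconcile these for an event that met the Week 12 rule in APD334-302 and ended there.

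**Working it through.** The plan has no figure to reproduce here; SAP Section 7 says there is no formal sample size estimation. The check compares the rules.

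**1. New use or increase falling wholly between Weeks 12 and 40, Week 52 endpoints**

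| Group | First listing | Second listing | Listings disagree for |
|---|---|---|---|
| Other small molecules | any exposure | more than 5 days | 1 to 5 days |
| Oral/rectal glucocorticoids | any dose above baseline | more than 7 days | 1 to 7 days |
| Parenteral glucocorticoids | any exposure | more than one dose | a single dose |
| Budesonide | any dose above baseline | more than 5 days | 1 to 5 days |
| Beclomethasone | any dose above baseline | more than 5 days | 1 to 5 days |

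All five groups conflict. Longer courses count as rescue under both listings, and so does new use after Week 40.

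**2. Could the first listing be a Week 12 rule only?** No, because it also differs from the second listing's own Week 12 rules, up to Week 8, in three groups.

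- Small molecules: any exposure against more than 5 days. Three days of tofacitinib at Week 4 is rescue under one listing only.
- Budesonide, for subjects not taking it at baseline: "more than 9 mg/day for one day or any exposure for more than 5 days" in the first listing. The second listing has no one-day dose trigger.
- Beclomethasone: a one-day trigger above 5 mg/day in the first listing only.

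The Week 12 rules for oral/rectal and parenteral glucocorticoids agree.

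**3. Window.** Day 281 − Day 85 = 196 days = 28 weeks, and 28/40 = 70% of the treatment period.

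**4. Weight of one reclassified remitter.** Inputs are about 35 subjects (Protocol synopsis) and 2:1 allocation in the parent study (Protocol 6.1). 35 × 2/3 ≈ 23, which gives an assumed 23:12 split. SAP 6.5 says allocation within Japan was not controlled, so two other assumed splits are shown.

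| Split (etrasimod:placebo) | Etrasimod | Placebo |
|---|---|---|
| 20:15 | 100/20 = 5.0 points | 100/15 = 6.7 points |
| 23:12 | 100/23 = 4.3 points | 100/12 = 8.3 points |
| 26:9 | 100/26 = 3.8 points | 100/9 = 11.1 points |

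Illustration with assumed counts:

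- 8/23 − 2/12 = 18.1 points
- one etrasimod remitter reclassified: 7/23 − 2/12 = 13.8 points
- one placebo remitter reclassified: 8/23 − 1/12 = 26.4 points

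Fisher p is 0.434, 0.450 and 0.121 respectively.

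**5. Weeks 16 to 48.** SAP 16.2 has four symptom endpoints at these visits, and the second listing has no rule for them. Protocol 9.4 scores such visits from the 3 (or 2) most recent consecutive diary days in the 7 days before the visit. If the Week 52 rule were borrowed, a subject on day 5 of tofacitinib at the Week 20 visit would not be on rescue and could count as a responder, although treatment overlaps the days scored.

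**6. Events before Week 12.** Read literally, the Week 52 windows leave them out. SAP 16.1.2 would carry them forward if its reference to the study includes APD334-302. SAP 2.5 limits this SAP to Week 16 to Week 52 data, which supports the narrower reading. The timing example in Appendix 6 covers only rescue started between the Week 12 and Week 52 assessments, so it does not settle the matter.

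**The case against.** **One list, finalised blinded.** The classification is completed before unblinding, so the ambiguity cannot be resolved by treatment assignment. This stands. It rules out inferring that the duplication favours etrasimod. It does not make the classification reproducible from the plan.

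**Few subjects, perhaps none.** To change the primary result, a subject must take a short course between Weeks 12 and 40, stay in the study and be in remission at Week 52. This also stands. The 70% is calendar time, and reading it as a probability of misclassification would be wrong.

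**The stricter listing may be the intended one.** Protocol 10.4 makes subjects who start a disallowed agent that can affect efficacy, or who increase a dose for worsening symptoms, nonresponders thereafter. It gives no 5-day or 7-day allowance. Its alternative, per-protocol handling, is unavailable because SAP 5.4 drops that analysis. Tofacitinib is prohibited (Protocol 6.7.3), and oral corticosteroids should not be newly started (Protocol 6.7.2.1). This has force: the labelled listing matches the immunosuppressant and 5-ASA format, but format does not show that it was meant to govern. The stricter rule should therefore be reported too.

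**Events before Week 12.** A reader might infer that the SAP says nothing about them, or that only immunosuppressants and 5-ASA are affected. Neither holds. SAP 16.1.2 does address later timepoints, and every class whose Week 52 window opens after Week 12 is in the same position. The provisions are unreconciled, not absent. Whether parent-study events count is partly a scope choice for the sponsor, since SAP Section 4 sends the integrated analysis to a separate plan.

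**Conclusion.** The plan states two contradictory rescue rules for five drug groups and does not say which applies. This is wrong as written and should be corrected before unblinding. The conflict covers courses of 1 to 5 days (three groups), 1 to 7 days (oral/rectal glucocorticoids) or a single parenteral dose, between Weeks 12 and 40. The Week 12 rules also differ for small molecules, budesonide and beclomethasone.

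The number of subjects affected is unknown and may be zero. Across the assumed splits, each reclassified remitter is worth 3.8 to 5.0 points on etrasimod or 6.7 to 11.1 points on placebo. The effect on the treatment difference could go either way. A reader might infer that a significance claim is at risk. The documents do not support that: Protocol 10.12.1 excludes hypothesis testing of efficacy, and the SAP's p-values are nominal and unadjusted for multiplicity. The assumptions are the planned size of about 35, the splits shown, and reviewers who remain blinded although Protocol 6.5 allows APD334-302 to be unblinded during this study.

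**What to change.** Before unblinding:

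1. **One rule per class.** Delete the unlabelled first listing for the five groups and keep the endpoint-labelled rules for Week 12 and Week 52 endpoints. The downside is that short courses between Weeks 12 and 40, such as up to 5 days of tofacitinib, then pass as non-rescue, an allowance Protocol 10.4 does not give. Repeat the primary and key secondary analyses under the stricter first-listing rule as a sensitivity analysis.
2. **Weeks 16 to 48.** Do not extend the Week 52 allowance to these symptom endpoints. Count as nonresponse any new use or dose above baseline that is ongoing at the visit or falls in the diary days scored for it.
3. **Carry-forward.** Add one clause, covering every class whose Week 52 window opens after Week 12, that says whether an event meeting the Week 12 rule in APD334-302 carries forward to Week 52. Word it to agree with Table 1 and 16.1.2.
4. **Re-run the blinded classification** under the single rule set.

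The cost is SAP wording, one blinded re-check in a process Appendix 6 already repeats until database lock, and a second rescue flag for the sensitivity analysis. If events carry forward, episodes that ended before transition must come from the APD334-302 record, because Protocol 6.7 brings only therapy ongoing at transition into the APD334-308 eCRF. Carry-forward may also reduce the number of Week 52 responders.
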